Subjects undergo a screening period that may last up to four weeks (Visit 0). Eligible subjects then undergo the PLC/KET Test Infusion (Visit 1) and undergo evaluation of treatment response 24 hours following the infusion (Visit 2). For subjects who meet criteria to continue in the study, they are randomized to one of two treatment conditions (PLC/KET or NP/KET) to take place up to four weeks from the Test Infusion (Visit 3). Subjects will again return for evaluation 1 week (+/- 2 days) following Visit 1(Visit 2a). After the second infusion (Visit 3), subjects will return for evaluation at 24 hours (Visit 4) and 1 week (+/- 2 days) following Visit 3 (Visit 5). Subjects will return for a final exit visit (Visit 6) 14 days (+/- 2 days) following the second infusion (Visit 3). Therefore, the total study participation time will be up to 10 weeks.

We anticipate a 2-year project period, during which time approximately 100 patients will be screened, with 40 patients randomized. However, after 8 patients have completed the study, the results will be unblinded to an independent statistician and an interim analysis conducted. On this basis, the study may be terminated, or it may be continued towards the goal of randomizing 40 total patients. A second interim analysis will be conducted once the sample size has doubled, and 16 patients have completed the study. The statistician will receive de-identified coded data only.

e) Study Endpoints

Primary Outcomes

- (a) Change in Montgomery–Asberg Depression Rating Scale (MADRS) compared across PLC/KET and NP/KET administrations.
- (b) Change in four-item positive symptom subscale of the Brief Psychiatric Rating Scale (BPRS), Clinician-Administered Dissociative States Scale (CADSS) and Visual Analog Scale (VAS) scores from Time 0 to Time 40 minutes compared across PLC/KET and NP/KET administrations.

 Mount Sinai	Protocol Title:	Pharmacologic attenuation of ketamine using nitroprusside
	Principal Investigator Name/Contact Info:	[name]/ [contact]
	Primary Contact Name/Contact Info	[name] / [contact]
	Date Revised:	4/15/2019
	Study Number:	HSM#16-00928/GCO#16-1580

Secondary Outcome

Change in molecular profiles obtained from blood draws of subjects at set time points that parallel clinical ratings during infusions of the agents under investigation and post-infusion follow up.

Statistical Analysis

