The null hypotheses of this study are that (a) pre-treatment with NP does not attenuate the antidepressant effects of KET (b) pre-treatment with NP does not reduce psychotic rating scores induced by KET, and (c) there are no changes in molecular measurements over the course of KET and/or NP infusions that correlate with clinical ratings. These hypotheses will be tested against their corresponding alternatives, namely that pre-treatment with NP effectively attenuates both the antidepressant and pro-psychotic effects of KET and that molecular changes in reflecting real-time changes in mental status can be tracked using serial blood draws.

Data will be analyzed using repeated measures General Linear Models with Time and Treatment Condition as within-subject variables. Overall F tests for significance will be followed up by post-hoc t-tests comparing rating scores between the treatment conditions.

The statistician will receive de-identified coded data only.

f) Procedures Involved in the Human Research

The current protocol consists of 8 study visits, as well as a phone call check-in (Study Visit 0: Screening; Study Visit 1: PLC/KET infusion; Study Visit 2: 24-hour follow-up of Study Visit 1; Study Visit 2a: 7-day follow-up of Study Visit 1; Phone-call follow-up of Study Visit 1; Study Visit 3: PLC/KET or NP/KET infusion; Study Visit 4: 24-hour follow-up of Study Visit 3; Study Visit 5: 7-day follow-up of Study Visit 3; Study Visit 6: study exit evaluation). Below, we first outline procedures for study drug administration that apply to both Study Visits 1 and 3. Then, we describe in more detail the procedures that will occur on each of the Study Visits. See Table 1 for an outline of the events occurring at all visits.

Description of Study Drug Procedures

 Mount Sinai	Protocol Title:	Pharmacologic attenuation of ketamine using nitroprusside
	Principal Investigator Name/Contact Info:	[name]/ [contact]
	Primary Contact Name/Contact Info	[name] / [contact]
	Date Revised:	4/15/2019
	Study Number:	HSM#16-00928/GCO#16-1580

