Study drugs are administered on Study Visits 1 (single-blind) and 3 (double-blind). Visits 1 and 3 will occur up to four weeks apart to allow subject depression levels to return to baseline, a necessary component of the study design in order to test whether NP has any effect on the antidepressant action of KET. At Visit 1, participants will receive single-blind placebo (PLC) followed by KET (0.5 mg/kg/hour for 40 minutes), in which they are blind to the PLC/NP condition but are aware they are receiving KET. Subjects return to the clinic 24 hours following Visit 1, at which time their eligibility to continue and be randomized in the study is determined. The criteria for continuing is a significant antidepressant response to KET as demonstrated by MADRS score of $\geq 50\%$ improvement from baseline. Eligible subjects are randomized to one of two treatment conditions for Visit 3 (double-blind): PLC/KET or NP/KET (NP dose: 0.5 micrograms/kg/minute for 240 minutes), where again, the blinded condition is PLC/NP, but the subjects are aware they are receiving KET. Ineligible subjects (i.e., ketamine non-responders) will be scheduled to return to the clinic for an exit visit 1 week (7 ± 2 days) following the first infusion. The appearance of the nitroprusside will be protected to allow this drug to be blinded. Given the potential lengthy duration between visits (between 2 and 4 weeks), subjects will return to the clinic approximately 1 week (7 ± 2 days) following V1 (PLC/KET) for a check-in (Visit 2a) with the study doctor in order to ensure subject safety, as well as to be evaluated for remission of depressive symptoms. Additionally, a phone call MADRS will be administered 3 to 4 days following the in-person check-in, which will serve as the final determinant of the subject's return to baseline (defined as receiving a score within 20% of the baseline MADRS). If the subject has not returned to baseline, the V3 will be rescheduled for a date approximately two weeks following its initial appointment in order to allow maximum time (4 weeks) for a return to baseline, and the two check-ins (Visit 2a and by-phone check-in) will be repeated for the next two weeks, for a total of 4 additional check-ins. Following the V3 infusion visit, subjects again return to the clinic at 24 hours (Visit 4) and at 7 ± 2 days (Visit 5) following the second infusion day, and once more 14 ± 2 days after the infusion for the Exit Visit (Visit 6).

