- *Blood draws before/after infusion (if applicable)*
- *Clinical ratings before/during/following infusion*

Study Visit 1 will occur up to 4 weeks after Study Visit 0. At this Visit, all participants will first receive PLC for Infusion 1 and KET for Infusion 2. Details of the dosing and timing for these infusion sequences, as well as the associated clinical ratings and blood draws, is explained in the “Description of Study Drug Procedures” section above.

Study Visits 2 and 4 (24-h follow ups)

Participants will return to the study site 24 hours after Study Visit 1 for Study Visit 2. At this visit, safety and efficacy assessments will be performed (no drugs will be administered). The research team will analyze the outcomes of the MADRS and CADDs for each participant obtained on this day. In order to best assess the capacity of NP to attenuate the pro-psychotic and antidepressant effects of KET, only those participants who show improvement in MADRS $\geq 50\%$ compared to baseline will be eligible to return for Study Visit 3.

 Mount Sinai	Protocol Title:	Pharmacologic attenuation of ketamine using nitroprusside
	Principal Investigator Name/Contact Info:	[name]/ [contact]
	Primary Contact Name/Contact Info	[name] / [contact]
	Date Revised:	4/15/2019
	Study Number:	HSM#16-00928/GCO#16-1580

Participants who meet these criteria will return for Study Visit 3 up to 4 weeks later (depending on the amount of time required for the patient's MADRS score to return to baseline). These participants will be randomized to receive a drug administration sequence of either PLC/KET or NP/KET at Study Visit 3.

All patients who return for Study Visit 3 will return to the study site within 24 hours for Study Visit 4. At this visit, safety and efficacy assessments will be performed (no drugs will be administered).

Study Visits 2a and 5 (7-day follow-ups) and Phone Call Check-In

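### The planned model treats the randomised comparison as within-subject, so its PLC/KET comparator is Visit 1, which was selected for a 50% MADRS response and biases Aim I towards attenuation

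*Combined protocol and SAP*

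**What the plan says.** The Statistical Analysis text in section 5e names one model for all outcomes: "Data will be analyzed using repeated measures General Linear Models with Time and Treatment Condition as within-subject variables". It continues: "Overall F tests for significance will be followed up by post-hoc t-tests comparing rating scores between the treatment conditions". The first primary outcome in the same section is change in the depression scale ("MADRS) compared across PLC/KET and NP/KET administrations"). Neither text says which visit supplies the PLC/KET data, or whether the t-tests are paired.

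The design is set out in three other places.

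- Section 5d: responders to the test infusion continue, and "they are randomized to one of two treatment conditions (PLC/KET or NP/KET) to take place up to four weeks from the Test Infusion".
- Section 5f, Description of Study Drug Procedures: "Study drugs are administered on Study Visits 1 (single-blind) and 3 (double-blind"), and "Eligible subjects are randomized to one of two treatment conditions for Visit 3 (double-blind): PLC/KET or NP/KET".
- Section 5f, Study Visits 1 and 3: of Visit 1 it says "At this Visit, all participants will first receive PLC for Infusion 1 and KET for Infusion 2". Under Study Visits 2 and 4, "only those participants who show improvement in MADRS" of at least 50% at 24 hours may go on to Visit 3.

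The goal in section 5c is 40 randomised. Alpha, power, SD, effect size and allocation ratio are not stated.

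**The concern.** Randomisation happens once and applies to Visit 3 only, so treatment is a between-subject factor. The drug sequence mentioned in section 5f is Infusion 1 then Infusion 2 within a single visit, not a crossover order. A participant in the PLC/KET arm receives PLC/KET twice and has no within-subject treatment contrast. A participant in the NP/KET arm has one, Visit 3 against Visit 1, and it is not randomised.

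For Aim I, Visit 1 enters that contrast only if its MADRS response reached 50%. Unless a participant's two responses are perfectly correlated, the mean response falls at Visit 3 with no help from nitroprusside. That fall has the same sign as Research Hypothesis I, so an inert drug could be reported as blunting ketamine's antidepressant effect.

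For Aim II the selection acts on MADRS and not directly on BPRS, CADSS or VAS. The Visit 1 versus Visit 3 comparison is still confounded with order of exposure and with single-blind against double-blind conditions. No direction or size is claimed there.

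**Working it through.** **Plan's own figure.** The 40 cannot be reproduced, because no inputs are given for it.

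**Assumed inputs (none in the document).** Nitroprusside inert; 20 per arm; baseline MADRS mean 32, SD 5; 24-hour improvement with the same mean m (16 or 19) and SD 9 after both infusions, independent of baseline; Visit 1 to Visit 3 correlation r of 0.3, 0.5 or 0.7. The 50% rule comes from section 5f.

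**Step 1: who continues.** A participant continues if improvement minus half of baseline is at least 0. That quantity has mean m − 16 and SD √(9² + 2.5²) = √87.25 = 9.34.

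- m = 16: Φ(0) = 50% respond, so 40/0.50 = 80 must be infused to randomise 40.
- m = 19: Φ(3/9.34) = Φ(0.321) = 62.6% respond, so 40/0.626 = 64 must be infused.

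Both are compatible with about 100 consented (section 5c), but this is weak support because the expected screen-failure rate is not given.

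**Step 2: the fall caused by selection.** Mean Visit 1 improvement among responders exceeds m by (81/9.34) × λ, where λ = φ(k)/Φ(k) and k = (m − 16)/9.34.

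- m = 16: λ = 0.798, excess 6.92 points.
- m = 19: λ = 0.605, excess 5.25 points.

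Only the fraction r of this excess carries over to Visit 3, so the expected fall is (1 − r) × excess.

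**Step 3: error rates by simulation.** Each scenario used a pool of 800,000 patients, the 50% rule, and 20,000 trials of 20 per arm. The rates count a significant result in the direction of attenuation at two-sided 0.05, so the nominal rate is 2.5%.

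| m | r | Fall (points) | NP arm, Visit 3 v own Visit 1 | Subject-effects model, both arms | All PLC/KET administrations pooled |
|---|---|---|---|---|---|
| 16 | 0.3 | 4.84 | 58% | 56% | 37% |
| 16 | 0.5 | 3.46 | 42% | 41% | 24% |
| 16 | 0.7 | 2.08 | 26% | 26% | 12% |
| 19 | 0.3 | 3.67 | 36% | 36% | 24% |
| 19 | 0.5 | 2.62 | 27% | 26% | 16% |
| 19 | 0.7 | 1.57 | 17% | 17% | 8% |

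The own-Visit-1 column is a paired t-test. With two time points, the Time-by-Treatment F is its square. The pooled column compares 20 NP/KET administrations with 60 PLC/KET administrations as if independent; 40 of those 60 (67%) are Visit 1.

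- At r = 0.9 the rates fall to 8–11% (own Visit 1) and about 3% (pooled).
- Adding a floor at a score of 0 and the section 5f rule of return to within 20% of baseline (baseline correlation 0.8 assumed) gives 20–66% and 10–42%. Restoring the starting level does not undo selection on the Visit 1 response.
- Between-arm tests stay at 4.7–5.5% two-sided (nominal 5%) in these scenarios, whether on Visit 3 alone, on the Visit 1 to Visit 3 change, or by ANCOVA.

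**Step 4: a second set of inputs.** Here the outcome is percentage improvement (mean 40–60, SD 25–30, r 0.3–0.9). At mean 50, SD 30 and r = 0.5, responders average 50 + 30 × 0.798 = 73.9% at Visit 1 and 50 + 0.5 × 23.9 = 62.0% at Visit 3, a fall of 12 percentage points. Over the whole range the paired test rejects in 9–87% of trials (two-sided, nominal 5%), and the between-arm Visit 3 test in 4.4–5.6%.

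**The case against.** The plan never says that Visit 1 is the comparator. The outcome wording about administrations could mean pooling, and the post-hoc t-tests could be run between arms at Visit 3. The percentages depend on inputs absent from the document and on a two-time-point test, whereas MADRS is collected more often; an F test over more time points was not simulated. At a correlation of 0.9 the pooled error is essentially nominal. At the smaller interim samples (4 and 8 per arm, assuming an even split of the 8 and 16 completers) the own-Visit-1 error is lower, about 5–11% and 8–24% on the Step 1 inputs with r from 0.3 to 0.7. Nothing is quantified for Aim II.

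Most of this limits how far the percentages can be pressed. It does not remove the mismatch. Visit 1 is the only PLC/KET exposure an NP/KET participant has, so a within-subject contrast must use it. Pooling still leaves two thirds of the comparator selected. A between-arm t-test would be valid, but the plan does not specify one, and as written it follows an F test from a model that does not fit the design.

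**Conclusion.** The concern holds and must be fixed. The contradiction between the model and the randomisation is in the text and needs no assumption. The direction of the Aim I bias, towards Research Hypothesis I, needs only an imperfect correlation between the two responses. Its size does depend on assumptions: with inert nitroprusside, 20 per arm and correlation 0.3 to 0.7, the fall is 1.6 to 4.8 MADRS points. False attenuation is 17–58% against own Visit 1 and 8–37% with pooling, against 2.5%. These figures apply to the readings simulated, not to every test the wording could allow. For Aim II the confounding is structural and no size is given.

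**What to change.** In section 5e, make randomised arm a between-subject factor and keep Time within-subject. Base the primary treatment test on the between-arm difference in response to the Visit 3 infusion: MADRS at Visit 4 (24 hours) for Aim I, and the Visit 3 infusion-day ratings for Aim II. The outcome definition names no MADRS time point. Visit 4 is proposed because it mirrors the assessment used to select responders. The Aim II time window is a separate matter and is left as it is.

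Bring in Visit 1 either as a covariate or through an arm-by-visit interaction. Both are valid, because selection affects the two arms equally; name one as primary in advance. Do not use Visit 1 as the PLC/KET comparator, alone or pooled with Visit 3. State that the post-hoc t-tests compare randomised arms, and reword the primary outcomes to match.

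Add one sentence defining any pre-infusion MADRS covariate on the same items as the outcome. The infusion-day version drops sleep and appetite, leaving 8 items scored 0–6 (range 0–48, not 0–60).

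The cost is wording, with no new visit or data, and lower apparent precision than a paired test. With an assumed SD of 9, detecting 8 points with 80% power needs 2 × 81 × (1.960 + 0.842)² / 64 = 19.9, so 20 per arm by the normal approximation. The exact t-test at 20 per arm has 78% power.

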Each treatment day (Visit 1 and 3) involves Infusion 1 (PLC or NP) and Infusion 2 (KET). Prior to Infusion 1 (PLC on Study Visit 1; PLC or NP on Study Visit 3) an indwelling catheter will be placed in the antecubital veins of each arm, and pulse, blood pressure, pulse-oximetry, and an EKG strip will be placed for continuous vital monitoring, which will be performed throughout the infusions. One of these catheters will be used for the administration of NP/PLC, and one will be used for the administration of KET; this is to ensure no interaction effects between the drugs given in the same line. At Time 0, Infusion 1 will begin through an infusion pump and will continue until Time 240 minutes. At Time 200

Protocol Title:	Pharmacologic attenuation of ketamine using nitroprusside
Principal Investigator Name/Contact Info:	[name]/ [contact]
Primary Contact Name/Contact Info	[name] / [contact]
Date Revised:	4/15/2019
Study Number:	HSM#16-00928/GCO#16-1580

minutes, Infusion 2 (KET on both Study Visits 1 and 3) will begin and will continue until Time 240 minutes, at which point all medication administration will be complete for the Study Visit. Clinical ratings (BPRS, CADSS, VAS; see below) will be collected at regular intervals before, during and after the infusion period by clinical raters. Blood draws may be conducted at baseline and Time +240 min on V1 and V3 infusion days, as well as at the 24-hour V2 and V4 visits, for a total of six blood draws; however, this is an optional procedure that will occur under a different protocol (GCO 11-1617). On the two infusion days, the blood will be drawn through one of the indwelling catheters that are used for study drug administration.

A urine toxicology screen will be performed before the first infusion and must be negative for illicit substances in order to proceed with the infusion. For females, a urine pregnancy test will confirm non-pregnancy prior to the infusions.

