The DSMB will ensure the safety of study participants and the integrity of the data collection in the projects. To achieve this goal, the DSMB will perform an ongoing evaluation of the safety of patients participating in the clinical outcomes in the clinical trial. This includes monitoring adverse events and overall clinical outcomes in the studies. Through this process the board will evaluate the need for study termination and/or modification of study criteria for inclusion, exclusion, or discontinuation. In

Protocol Title:	Pharmacologic attenuation of ketamine using nitroprusside
Principal Investigator Name/Contact Info:	[name]/ [contact]
Primary Contact Name/Contact Info	[name] / [contact]
Date Revised:	4/15/2019
Study Number:	HSM#16-00928/GCO#16-1580

addition, the DSMB will be responsible for the evaluation of the adherence to written protocols regarding the protection of human subjects and the assurance of identity protection as specified in the Data Sharing Section. The DSMB will expeditiously review all serious adverse events and perform ongoing scheduled reviews of non-serious adverse events and study dropouts. The DSMB includes the following members: The Oversight Committee members are to include: [name], Professor of Psychiatry, Brown University; [name], Icahn School of Medicine Professor of Anesthesiology; [name], Professor of Psychiatry, Icahn School of Medicine at Mount Sinai; and [name], Professor of Neurology and Professor of Anesthesiology, Icahn School of Medicine at Mount Sinai. The board will review the project's data and safety on bi-annual basis and report their findings to the PI.

i) Withdrawal of Subjects

Investigators may elect to withdraw the patient due to safety concern or non-adherence to the study protocol. Subjects may withdraw at any point in the study.

6) Risks to Subjects

Risks associated with NP [The following information was derived from the FDA package insert for NP (Nitropress [package insert]. Lake Forest, IL: Hospira Inc; 2014).]

The principal hazards of NP excessive hypotension and excessive accumulation of cyanide. Transient excesses in the infusion rate of NP can result in excessive hypotension, sometimes to levels so low as to compromise the

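### If Time for MADRS includes the 7-day and 14-day visits, the repeated-measures GLM as usually run discards recorded 24-hour scores that a mixed model would keep

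*Combined protocol and SAP*

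**What the plan says.** Section 5e, Statistical Analysis, gives the model: "Data will be analyzed using repeated measures General Linear Models with Time and Treatment Condition as within-subject variables". It continues: "Overall F tests for significance will be followed up by post-hoc t-tests comparing rating scores between the treatment conditions". Nothing else in the document describes the analysis of the clinical ratings. There is no analysis set, missing-data method, imputation rule or expected dropout rate.

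Primary outcome (a) in section 5e is change in MADRS "compared across PLC/KET and NP/KET administrations", with no time point. Primary outcome (b) covers the BPRS positive items, CADSS and VAS, and is given a window: "scores from Time 0 to Time 40 minutes compared across PLC/KET and NP/KET administrations".

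After the randomised infusion at Visit 3, patients return at 24 hours (Visit 4), 7 days (Visit 5) and 14 days (Visit 6), according to section 5d. Section 5f names MADRS explicitly at Visit 5 and refers to efficacy assessments at Visits 4 and 6. It also says that the infusion-day scales "will be collected at regular intervals before, during and after the infusion period by clinical raters". Section 5i states: "Subjects may withdraw at any point in the study". The goal in section 5c is 40 randomised patients.

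**The concern.** A classical repeated-measures GLM works on one complete row per patient. If one level of Time is blank, the usual software either removes the patient or refuses to run. With three follow-up visits over 14 days and withdrawal allowed at any point, some blanks should be expected. The patient removed for a missed day 14 may well have a recorded 24-hour MADRS, the same interval that the protocol uses to judge response to the first infusion.

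Two things are at stake. One is power, in a trial of 40 with no stated power calculation. The other is validity: a complete-case analysis is generally safe only when missingness is completely at random, whereas a likelihood-based mixed model that uses all recorded scores needs the weaker condition of missing at random. The plan names the more fragile method and has no rule that offsets its behaviour.

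**Working it through.** **Inputs from the document.** 40 randomised (section 5c). Post-infusion visits at 24 hours, 7 days and 14 days (section 5d).

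**Assumptions, because the document gives none of these.** 1:1 allocation, so 20 per arm; two-sided alpha 0.05; probability m of missing each of the three visits, independently; Time includes all three visits; 24 hours is the comparison of interest. A two-sample t-test stands in for the arm contrast at 24 hours.

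**The plan's own figure.** The 40 cannot be reproduced, since no effect size, SD, alpha or power is stated. For orientation, 20 per arm gives 80.0% power for a difference of 0.909 SD under the assumptions above.

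**Does the method behave this way?** Data were simulated for 20 patients under two conditions at three times, which is 120 ratings. Removing the 7-day score of two patients under one condition left 118. The repeated-measures ANOVA routine stopped because the data were unbalanced, and only 18 patients were complete, although all 20 had a 24-hour score. A mixed model ran on all 20 patients and 118 ratings.

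**Recorded 24-hour scores discarded.**

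- Scores recorded at 24 hours: 40 × (1 − m)
- Patients complete at all three visits: 40 × (1 − m)³
- Recorded scores discarded: the difference between the two

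| m | Recorded at 24 h | Complete | Discarded |
|---|---|---|---|
| 5% | 40 × 0.95 = 38.0 | 40 × 0.857 = 34.3 | 3.7 |
| 10% | 40 × 0.90 = 36.0 | 40 × 0.729 = 29.2 | 6.8 |

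**Power for 0.909 SD.** The fair comparison is complete cases against all recorded 24-hour scores under the same missingness. A mixed model cannot restore a 24-hour score that was itself missed.

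| m | All recorded 24-h scores | Complete cases | Loss due to the method |
|---|---|---|---|
| 5% | 19 per arm: 77.8% | 17.15 per arm: 73.3% | 4.5 points |
| 10% | 18 per arm: 75.5% | 14.58 per arm: 65.8% | 9.7 points |

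**Sensitivity to what Time contains.** With only the 24-hour and 7-day visits in Time, the discarded scores are 38 × 0.05 = 1.9 or 36 × 0.10 = 3.6. With only pre-infusion and 24 hours, a missed later visit discards none.

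**Sensitivity to independence.** If a fixed share m of the remaining patients drops out for good at each visit, the counts are the same, because 40 × (1 − m) still have a 24-hour score and 40 × (1 − m)³ still complete. If the same patients miss all three visits, no recorded 24-hour score is discarded.

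**The case against.** The strongest reply is that the harm depends on choices the plan has not made. Most of it stands as a limit on the claim:

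- **Complete-case deletion is not in the text.** A reader might infer that the plan commits to analysing only complete patients. It does not say so; that is how the named method is usually run.
- **Time is undefined.** Neither 24 hours nor any other visit is named for MADRS. A plan that used only pre-infusion and 24 hours would be untouched. Equally, nothing in the plan rules out the harmful reading.
- **The post-hoc t-tests might use every available score.** The plan is silent. Even so, they follow an overall F test that would not.
- **The infusion-day scales.** Ratings at many intervals might suggest the same loss there. Outcome (b), however, is a change between two times on one supervised day, and the plan does not say that the other intervals enter the model.
- **The size is easily overstated.** A reader might compare complete cases with a full 40 and read a fall from 80% to 73% or 66%. About a third of that fall (2.2 of 6.7 points, or 4.5 of 14.2) comes from 24-hour scores that were themselves missed, and no choice of model recovers those.
- **Bias.** One might infer that patients with a blunted response would skip later visits and so bias the result. The document gives no support for this. It is a possibility, not a finding.

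It can also be said that this belongs with the larger fault in the same sentence: Treatment Condition is declared within-subject, although patients randomised to PLC/KET at Visit 3 never receive NP/KET. The two should be corrected together. They remain separate, because making arm a between-subject factor while keeping the GLM would leave the deletion in place.

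**Conclusion.** The concern holds conditionally and mainly for MADRS. The only named method would, as usually run, remove patients with a recorded 24-hour score if Time includes later visits, and the plan neither excludes that reading nor has a missing-data rule to offset it.

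Under the stated assumptions, the avoidable loss is about 3.7 or 6.8 recorded scores out of 40, and roughly 5 or 10 points of power for a 0.909 SD difference, at 5% or 10% missed per visit. The loss is zero if Time stops at 24 hours. Allocation, alpha, miss rates and independence are all assumptions.

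This calls for a better choice of method that should be made before the data are analysed. It is not evidence that the planned result would be biased.

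**What to change.** In section 5e:

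1. State the MADRS time point for outcome (a) and list the visits that form Time.
2. Replace the repeated-measures GLM with a likelihood-based mixed model for repeated measures. Include randomised arm as a between-subject factor, time, arm-by-time and the pre-infusion score. Use unstructured covariance, with compound symmetry if that fails to converge, and Kenward-Roger degrees of freedom.
3. Use all available ratings after Visit 3 from every randomised, treated patient, and make the arm contrast at the named time point the primary test.
4. Make this change together with the correction of Treatment Condition as a within-subject factor. A mixed model alone does not define the randomised comparison.

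The cost is wording and a different standard procedure, with no new visits or data. The downside is that validity then rests on missing at random, which the data cannot verify and which the plan should state.

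### The randomised Visit 3 comparison is given no covariate adjustment, so each patient's own Visit 1 response to ketamine without nitroprusside, already collected, is not used to sharpen it

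*Combined protocol and SAP*

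**What the plan says.** All references are to the combined protocol.

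- **Randomisation** (5f, Description of Study Drug Procedures): "Eligible subjects are randomized to one of two treatment conditions for Visit 3 (double-blind): PLC/KET or NP/KET". Each patient therefore receives one of the two conditions at Visit 3, and the randomised contrast is between patients.
- **Visit 1** (5f, Study Visits 1 and 3): "all participants will first receive PLC for Infusion 1 and KET for Infusion 2". Every randomised patient has a response to ketamine without NP on record.
- **Endpoints** (5e, Primary Outcomes): both primary outcomes are changes. For BPRS, CADSS and VAS the definition is change in "scores from Time 0 to Time 40 minutes compared across PLC/KET and NP/KET administrations". For MADRS the two time points are not given.
- **Analysis** (5e, Statistical Analysis): "Data will be analyzed using repeated measures General Linear Models with Time and Treatment Condition as within-subject variables". Overall F tests come first, and then "post-hoc t-tests comparing rating scores between the treatment conditions".
- **Ratings** (5f): BPRS, CADSS and VAS are rated before, during and after the infusion period. The infusion-day MADRS omits two of its ten items, sleep and appetite.

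No section names a covariate, an ANCOVA, or any use of the Visit 1 response in the Visit 3 comparison. The protocol does not say whether the t-tests are paired or two-sample, or whether they use raw or change scores.

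**The concern.** The target is 40 randomised patients, and the protocol gives no power calculation. Patients may differ widely in how strongly ketamine affects them. A two-sample comparison at Visit 3 leaves that spread in its error term. The trial measures part of it directly at Visit 1, when the same patient receives ketamine with placebo, but the stated tests do not use that value.

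Using change scores does not remove the problem. Change uses the same-day starting score and not the Visit 1 response. Patients with a lifetime history of psychotic features are excluded, so BPRS positive scores before the infusions may sit near the floor. Change is then almost the raw post-ketamine score, and the spread in susceptibility remains.

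The stake is power and interval width, not bias or type I error. There is also a pre-specification gain: naming one estimator before unblinding prevents a later choice among raw, change and adjusted results.

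**Working it through.** **Inputs.** From the protocol: 40 randomised (5c) and interim looks after 8 and 16 completers (5d). The protocol gives no alpha, allocation ratio, SD, correlation, effect size or power, so there is no plan figure to reproduce. Assumed for illustration: 20 per arm, two-sided alpha 0.05, equal SDs, a true difference of 0.8 raw SD, and correlation ρ between covariate and outcome.

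**Step 1: variance of the arm difference, relative to raw scores.** Raw: 1. Change: 2(1−ρ). ANCOVA on one covariate: 1−ρ². Power is from the noncentral t, with 38 df (37 for ANCOVA).

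| ρ | Change, variance | Change, power | ANCOVA, variance | ANCOVA, power | Raw, power |
|---|---|---|---|---|---|
| 0.2 | 1.60 | 50% | 0.96 | 71% | 69% |
| 0.3 | 1.40 | 55% | 0.91 | 73% | 69% |
| 0.5 | 1.00 | 69% | 0.75 | 81% | 69% |
| 0.7 | 0.60 | 89% | 0.51 | 93% | 69% |

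Against change scores, adjusting for the same starting score cuts variance by 1 − 0.91/1.40 = 35%, 1 − 0.75/1.00 = 25% and 1 − 0.51/0.60 = 15% at ρ = 0.3, 0.5 and 0.7. Below ρ = 0.5, change is noisier than raw.

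**Step 2: cost of estimating covariates.** With N patients and k normally distributed covariates explaining a share R² of the within-arm variance, the variance ratio to raw becomes (1−R²)(N−3)/(N−k−3). The break-even is R² = k/(N−3).

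| N | k | Ratio, R² 0 | Ratio, R² 0.09 | Ratio, R² 0.25 | Break-even R² |
|---|---|---|---|---|---|
| 40 | 1 | 1.03 | 0.94 | 0.77 | 1/37 = 0.03 |
| 40 | 2 | 1.06 | 0.96 | 0.79 | 2/37 = 0.05 |
| 16 | 1 | 1.08 | 0.99 | 0.81 | 1/13 = 0.08 |
| 16 | 2 | 1.18 | 1.08 | 0.89 | 2/13 = 0.15 |
| 8 | 1 | 1.25 | 1.14 | 0.94 | 1/5 = 0.20 |
| 8 | 2 | 1.67 | 1.52 | 1.25 | 2/5 = 0.40 |

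Simulation agrees. With two covariates at N = 40, of which only the Visit 1 value is prognostic, power is about 71%, 78–79% and 92% at ρ = 0.3, 0.5 and 0.7. If neither is prognostic, power falls by about 2 points. Type I error stays near 5%. At N = 8 with two covariates, power falls from about 16% to 12–14% at R² of 0.09 to 0.25.

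**Step 3: which Visit 3 score may serve as covariate.** On an infusion day NP or placebo starts at Time 0 and ketamine at Time 200 minutes (5f). A rating taken just before ketamine can therefore follow 200 minutes of NP. It is post-randomisation, and adjusting for it can remove part of the effect. As an assumed example, suppose NP lowers that score by 0.4 SD and the slope is 0.5. A true 0.8 SD effect is then estimated as 0.8 − 0.5 × 0.4 = 0.60 SD. The covariate must be the score before Infusion 1.

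The BPRS, CADSS and VAS endpoint window ends at Time 40 minutes, while ketamine runs from Time 200 to Time 240. These two clocks must be reconciled before any score can be labelled.

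**The case against.** Much of the case on the other side stands, and it limits how far the point can be pushed.

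- **A reader might infer that the t-tests use raw scores.** The phrase rating scores invites this, but 5e defines both outcomes as change, and Time is a factor in the model, so a Time-by-Condition test is already a change contrast. The documents do not settle it.
- **A reader might infer that these t-tests decide the trial.** They are post-hoc to overall F tests, and no decision rule is stated.
- **A reader might infer that the loss occurs however the treatment factor is coded.** It does not. Read literally, a within-subject Treatment Condition compares each NP/KET patient with that patient's own Visit 1, which removes stable between-patient variance. On the assumptions above, with 20 pairs, that paired test has about 82%, 92% and 99% power at ρ = 0.3, 0.5 and 0.7. But it makes no use of the randomised control and is confounded with visit order and with selection of Visit 1 responders. The mismatch between this coding and the randomisation comes first; the covariate question concerns the randomised contrast.
- **A reader might infer that the return-to-baseline rule** ("defined as receiving a score within 20% of the baseline MADRS") **lets Visit 3 starting scores vary from 80% to 120% of baseline.** The final check is a telephone MADRS 3 to 4 days after the in-person check-in. It does not bound the Visit 3 score.
- **A reader might infer a large gain.** No correlation is given. Starting BPRS positive scores may add little, and the 50% response gate narrows the range of the Visit 1 MADRS response. Scenarios in which NP halves a stable individual response show large gains, but they assume that stability.

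An unadjusted comparison of randomised groups is valid, so this is a matter of efficiency. What survives is that no covariate is named, that the Visit 1 response goes unused in the randomised comparison, and that using it costs little at the final analysis.

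**Conclusion.** The point holds for the randomised between-patient comparison at Visit 3: the protocol specifies no adjustment there for values the trial already collects. This is true whether the t-tests use raw or change scores, because neither uses the Visit 1 response in that comparison.

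The size is illustrative. On the assumptions stated in the check, one covariate adds about 4, 12 or 24 points to a power of 69%, and two covariates slightly less. For BPRS, CADSS and VAS the Visit 1 response is probably the more useful covariate. For MADRS the gain is likely smaller.

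The cost is one or two degrees of freedom of 38 at the final analysis, and about 2 points of power if the covariates prove uninformative. At the interim looks adjustment can lose precision: at 8 completers even one covariate loses unless R² exceeds 0.20 (ρ about 0.45). The change is worth making, but its absence does not invalidate the analysis.

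**What to change.** Replace the t-test sentence in section 5e with wording such as:

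*For each primary outcome the NP/KET minus PLC/KET difference at Visit 3 will be estimated by ANCOVA (or the equivalent mixed model), adjusting for the Visit 3 value of the same scale taken before Infusion 1 starts (for MADRS, scored on the same item set as the outcome) and, for BPRS, CADSS and VAS, the corresponding Visit 1 PLC/KET response. The adjusted difference with its 95% CI is the primary result. At the analyses after 8 and 16 completers at most one covariate, named in advance, will be used.*

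Three things must accompany it:

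- state that Treatment Condition is a between-patient factor in this analysis;
- reconcile the endpoint clock in 5e with the infusion clock in 5f;
- name the MADRS time points and item set. If the 24-hour MADRS uses all ten items, rescore it on the 10 − 2 = 8 items shared with the infusion-day version, or define another baseline.

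This is a short text change and needs no new visits, provided each scale is rated before Infusion 1 on infusion days. It should be fixed before any unblinding, including the first interim look.
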